14.3.3 Narratives of Deaths, Other Serious and Significant Adverse Events

(not included in SAP, but this is a placeholder for the CSR)

14.4 Summary of Concomitant Medications

Table 30:Number and Percentage of Participants with Prior and Concurrent Medications by
WHO Drug Classification and Treatment Group

WHO Drug Code Level 1, Anatomic	WHO Drug Code Level 2, Therapeutic Subgroup	DBS (N=X)			SOC (N=X)		All Randomized (N=X)		vational =X)
Group		n	%	n	%	n	%	n	%
Any Level 1 Codes	Any Level 2 Codes	x	xx	x	xx	x	xx	x	xx
[ATC Level 1 - 1]	Any [ATC 1 – 1]								
	[ATC 2 - 1]								
	[ATC 2 - 2]								
	[ATC 2 - 3]								
[ATC Level 1 – 2]	[ATC 2 - 1]								
	[ATC 2 - 2]								
	[ATC 2 - 3]								
	nts in the Safety Population nts reporting taking at leas		tion in the spe	ecific WHO	Drug Class		•		

14.5 Participant and Provider Satisfaction Data

Table 31: Participant Questionnaire, After Third Training

[Implementation Note: Questions with responses on the Likert scale are converted to numeric as described in Section 3.3.12. For each question, the number of participants who selected a response other than "Prefer not to Answer" are summarized in the "Responses, n" row. For Yes/No questions, the number in the "Responses, n" row is the denominator for the "Yes, n (%)" row. The denominator for the rows under "If yes, describe" is the count from the number of participants who responded "Yes" to the previous question.]

Question	Statistic	After Second Training (N=X)
	Responses, n	Х
The self-collection teaching videos are helpful and easy to follow.	Mean (SD)	x.x (x.x)
	Median [Min, Max]	x [x, x]
	Responses, n	n=X
The CMV dried blood spot self-collection is easy.	Mean (SD)	x.x (x.x)
	Median [Min, Max]	x [x, x]
	Responses, n	n=X
After the training sessions, I feel confident collecting my own CMV dried blood spot samples.	Mean (SD)	x.x (x.x)
	Median [Min, Max]	x [x, x]
	Responses, n	n=X
After the training sessions, I feel confident about scheduling USPS pick- up for my sample.	Mean (SD)	x.x (x.x)
	Median [Min, Max]	x [x, x]
Do you foresee any problems with collecting dried blood spot samples	Responses, n	n=X
when you are back at home?	Yes, n (%)	xxx (xx%)
If yes, describe:		
Unable to reach caregiver	n (%)	xxx (xx%)
Inadequate supplies	n (%)	xxx (xx%)
Do not feel comfortable performing procedure	n (%)	xxx (xx%)
Technical difficulties	n (%)	xxx (xx%)

N=Number of participants in the DBS arm with questionnaire data available

Questions asked on the Likert scale are for agreement (1-Strongly Disagree, 2-Disagree, 3-Neither Agree nor Disagree, 4-Agree, 5-Strongly Agree) or frequency (1-Never, 2- Very Rarely, 3-Rarely, 4-Occasionally. 5-Very Frequently). Answers to questions asked on the Likert scale will be converted to numbers ranging from 1-5, or missing if Prefer Not To Answer was selected.

Table 32:Composite Scores of Participant Satisfaction, One Month Post-Discharge and After
Study Completion

[Implementation note: Composite scoring definitions are provided in Section 12.2. Responses on the Likert scale are converted to numeric as described in Section 3.3.12]

Composite Score	Statistic	One Month Post-Discharge (N=X)	After Study Completion (N=X)	
	Responses, n	Х	Х	
Overall satisfaction with email and mobile technology	Mean (SD)	x.x (x.x)	x.x (x.x)	
	Median [Min, Max]	x [x, x]	x [x, x]	
	Responses, n	n=X	n=X	
Overall satisfaction with kit contents, testing and shipping procedures	Mean (SD)	x.x (x.x)	x.x (x.x)	
	Median [Min, Max]	x [x, x]	x [x, x]	

N=Number of participants in the DBS arm with questionnaire data available

Questions asked on the Likert scale are for agreement (1-Strongly Disagree, 2-Disagree, 3-Neither Agree nor Disagree, 4-Agree, 5-Strongly Agree) or frequency (1-Never, 2- Very Rarely, 3-Rarely, 4-Occasionally. 5-Very Frequently). Answers to questions asked on the Likert scale will be converted to numbers ranging from 1-5, or missing if Prefer Not To Answer was selected.

Table 33: Participant Questionnaire, One Month Post-Discharge

[Implementation Note: Questions with responses on the Likert scale are converted to numeric as described in Section 3.3.12. For each question, the number of participants who selected a response other than "Prefer not to Answer" are summarized in the "Responses, n" row. For Yes/No questions, the number in the "Responses, n" row is the denominator for the "Yes, n (%)" row. The denominator for the rows under "If yes, describe" is the count from the number of participants who responded "Yes" to the previous question.]

Question	Statistic	One Month Post-Discharge (N=X)
	Responses, n	Х
The self-collection teaching videos are helpful and easy to follow.	Mean (SD)	x.x (x.x)
	Median [Min, Max]	x [x, x]
	Responses, n	n=X
The web or mobile phone site is easy to use and provides me with the information I need to do the testing at home.	Mean (SD)	x.x (x.x)
information r need to do the testing at nome.	Median [Min, Max]	x [x, x]
	Responses, n	n=X
The web or mobile phone options give me the choices I want for how and when I receive the reminders.	Mean (SD)	x.x (x.x)
	Median [Min, Max]	x [x, x]
	Responses, n	n=X
The email or mobile phone messages remind me to do the self-collection.	Mean (SD)	x.x (x.x)
	Median [Min, Max]	x [x, x]
	Responses, n	n=X
The self-collection kit had everything I needed to do the testing.	Mean (SD)	x.x (x.x)
	Median [Min, Max]	x [x, x]
	Responses, n	n=X
The CMV dried blood spot self-collection is easy.	Mean (SD)	x.x (x.x)
	Median [Min, Max]	x [x, x]
	Responses, n	n=X
Did you need any help from another person to collect your dried blood spot?	Yes, n (%)	xxx (xx%)
	Responses, n	n=X
Scheduling USPS to pick up my sample is easy.	Mean (SD)	x.x (x.x)
	Median [Min, Max]	x [x, x]
	Responses, n	n=X
Did you have any trouble scheduling USPS mail pick up?	Yes, n (%)	xxx (xx%)
If yes, select best response:		
Application failed and could not schedule	n (%)	xxx (xx%)
Difficulty navigating portal to schedule	n (%)	xxx (xx%)
Forgot to schedule pick up	n (%)	xxx (xx%)
Pick up did not occur	n (%)	xxx (xx%)
Pick up occurred but was more than 4 hours after the scheduled time	n (%)	xxx (xx%)

Question	Statistic	One Month Post-Discharge (N=X)
Unable to connect to USPS website	n (%)	xxx (xx%)
Unable to call USPS to schedule the pick-up	n (%)	xxx (xx%)
	Responses, n	n=X
Did you miss any DBS collections thus far?	Yes, n (%)	xxx (xx%)
Reasons for not collecting DBS at any time during the study	Responses, n	n = X
I was too busy to do the self collection	Mean (SD)	x.x (x.x)
	Median [Min, Max]	x [x, x]
	Mean (SD)	x.x (x.x)
I did not feel well enough	Median [Min, Max]	x [x, x]
	Mean (SD)	x.x (x.x)
I forgot or collection reminder failed	Median [Min, Max]	x [x, x]
	Mean (SD)	x.x (x.x)
I was hospitalized or had health complications	Median [Min, Max]	x [x, x]
	Mean (SD)	x.x (x.x)
I was on holiday or vacation	Median [Min, Max]	x [x, x]
	Mean (SD)	x.x (x.x)
I did not have caregiver's help	Median [Min, Max]	x [x, x]
	Mean (SD)	x.x (x.x)
I lost interest in the study	Median [Min, Max]	x [x, x]
What would make the dried blood spot testing work better for you?	Responses, n	n = X
More frequent testing	n (%)	xxx (xx%)
Less frequent testing	n (%)	xxx (xx%)
Clearer written instructions	n (%)	xxx (xx%)
More training sessions with coordinator	n (%)	xxx (xx%)
No changes are needed	n (%)	xxx (xx%)
What would make the videos work better for you?	Responses, n	n = X
Structure or content	n (%)	xxx (xx%)
Shorter length	n (%)	xxx (xx%)
Effective DBS demonstration	n (%)	xxx (xx%)
Pace of instruction	n (%)	xxx (xx%)
No changes are needed	n (%)	xxx (xx%)
What would make the reminders work better for you?	Responses, n	n = X
Phone call reminders	n (%)	xxx (xx%)
Content of the reminder	n (%)	xxx (xx%)
More frequent reminders	n (%)	xxx (xx%)
Flexibility in reminder day	n (%)	xxx (xx%)
No changes are needed	n (%)	xxx (xx%)

Question	Statistic	One Month Post-Discharge (N=X)
What can we improve?	Responses, n	n = X
Training	n (%)	xxx (xx%)
DBS Test kit supplies	n (%)	xxx (xx%)
Data entry	n (%)	xxx (xx%)
DBS testing Reminders	n (%)	xxx (xx%)
No changes are needed	n (%)	xxx (xx%)

N=Number of participants in the DBS arm with questionnaire data available.

Questions asked on the Likert scale are for agreement (1-Strongly Disagree, 2-Disagree, 3-Neither Agree nor Disagree, 4-Agree, 5-Strongly Agree) or frequency (1-Never, 2- Very Rarely, 3-Rarely, 4-Occasionally. 5-Very Frequently). Answers to questions asked on the Likert scale will be converted to numbers ranging from 1-5, or missing if Prefer Not To Answer was selected.

Table 34: Participant Questionnaire, After Study Completion

[Implementation Note: Questions with responses on the Likert scale are converted to numeric as described in Section 3.3.12. For each question, the number of participants who selected a response other than "Prefer not to Answer" are summarized in the "Responses, n" row. For Yes/No questions, the number in the "Responses, n" row is the denominator for the "Yes, n (%)" row. The denominator for the rows under "If yes, describe" is the count from the number of participants who responded "Yes" to the previous question.]

Question	Statistic	After Study Completion (N=X)		
	Responses, n	Х		
[Question on the Likert Scale]	Mean (SD)	x.x (x.x)		
	Median [Min, Max]	x [x, x]		
What can we improve?	Responses, n	n = X		
Training	n (%)	xxx (xx%)		
DBS Test kit supplies	n (%)	xxx (xx%)		
Data entry	n (%)	xxx (xx%)		
DBS testing Reminders	n (%)	xxx (xx%)		
No changes are needed	n (%)	xxx (xx%)		

N=Number of participants in the DBS arm with questionnaire data available

Questions asked on the Likert scale are for agreement (1-Strongly Disagree, 2-Disagree, 3-Neither Agree nor Disagree, 4-Agree, 5-Strongly Agree) or frequency (1-Never, 2- Very Rarely, 3-Rarely, 4-Occasionally. 5-Very Frequently). Answers to questions asked on the Likert scale will be converted to numbers ranging from 1-5, or missing if Prefer Not To Answer was selected.

Table 35: Provider Questionnaire, After Study Completion

[Implementation Note: Questions with responses on the Likert scale are converted to numeric as described in Section 3.3.12. For each question, the number of participants who selected a response other than "Prefer not to Answer" are summarized in the "Responses, n" row. For Yes/No questions, the number in the "Responses, n" row is the denominator for the "Yes, n (%)" row. The denominator for the rows under "If yes, describe" is the count from the number of participants who responded "Yes" to the previous question.]

Question	Statistic	After Study Completion (N=X)
	Responses, n	X
Overall satisfaction with CMV dried blood spot self-collection results ^a	Mean (SD)	x.x (x.x)
	Median [Min, Max]	x [x, x]
	Responses, n	X
DBS testing will increase adherence to CMV surveillance late after HCT.	Mean (SD)	x.x (x.x)
	Median [Min, Max]	x [x, x]
	Responses, n	n=X
The results of the finger stick CMV self-collection were available to me n an easy and timely fashion.	Mean (SD)	x.x (x.x)
	Median [Min, Max]	x [x, x]
	Responses, n	n=X
I was confident with the results of the CMV dried blood spot self-	Mean (SD)	x.x (x.x)
	Median [Min, Max]	x [x, x]
	Responses, n	n=X
f I have the results of the CMV self-collection, I do not feel I need an additional plasma blood draw to decide on treatment for my patient	Mean (SD)	x.x (x.x)
	Median [Min, Max]	x [x, x]
	Responses, n	n=X
would participate in another study with use of this type of blood self-	Mean (SD)	x.x (x.x)
	Median [Min, Max]	x [x, x]

N=Number of Participants in the DBS arm with questionnaire data available

The primary care providers of each participant should have been sent a provider questionnaire at the time of the participant's last quarterly follow-up records request.

Questions asked on the Likert scale are for agreement (1-Strongly Disagree, 2-Disagree, 3-Neither Agree nor Disagree, 4-Agree, 5-Strongly Agree) or frequency (1-Never, 2- Very Rarely, 3-Rarely, 4-Occasionally. 5-Very Frequently). Answers to questions asked on the Likert scale will be converted to numbers ranging from 1-5, or missing if Prefer Not To Answer was selected. ^a The composite score is calculated from the Likert scale values.

14.6 Testing and Technology Data

Table 36:Time Between Scheduled Sample Pick-Up and Arrival at Study Laboratory, by Site and
Perceived Ease of Access to Blood Draw Facility

Perceived Ease of Access to Blood Draw Facility	Variable	Statistic	Fred Hutchinson Cancer Research Center (N=X)	Memorial Sloan Kettering Cancer Center (N=X)	University of Minnesota (N=X)	MD Anderson Cancer Center (N=X)	All Sites (N=X)
Easy	Samples with shipment time and arrival time entered	n	Х	Х	Х	Х	Х
	Hours from	Mean (SD)					
	scheduled pick-up to arrival	Median [Min, Max]					
Difficult	Samples with shipment time and arrival time entered	Number					
	Hours from	Mean (SD)					
	scheduled pick-up to arrival	Median [Min, Max]					
Any Difficulty	Samples with shipment time and arrival time entered	Number					
	Hours from	Mean (SD)					
	scheduled pick-up to arrival	Median [Min, Max]					

Specimen shipment information is participant-entered data and may possess inaccurate shipment times or not have been entered for specimens. Any specimens received by the lab lacking shipment information or with a shipment time less than or equal to arrival time are excluded from this analysis.

Table 37:Number of Scheduled DBS Unevaluable Due to Lack of Amplification or Inhibition, by
Site

Statistic	Fred Hutchinson Cancer Research Center (N=X)	Memorial Sloan Kettering Cancer Center (N=X)	University of Minnesota (N=X)	MD Anderson Cancer Center (N=X)	All Sites (N=X)
Sample pick-ups scheduled ^a , n	XXX	XXX	XXX	XXX	XXX
Samples received, n	XXX	XXX	XXX	XXX	XXX
Number of participants with unevaluable samples, n (%°)	XXX (xx%)	XXX (xx%)	XXX (xx%)	XXX (xx%)	XXX (xx%)
Number unevaluable samples, n (% ^b)	XXX (xx%)	XXX (xx%)	XXX (xx%)	XXX (xx%)	XXX (xx%)

N=Number of participants in the DBS arm in the ITT Population.

^a Specimen shipment information is participant-entered data and may not have been entered for specimens, resulting in the number of specimens shipped being less than the number of specimens received and entered into the data system by the testing lab.

^b Relative to number of samples received.

^cAn unevaluable sample is the equivalent of sample viability failure.

Table 38: Concordance between Confirmatory WB and Confirmatory DBS Testing

Statistic	DBS Participants with Concordance Samples (N=X)
Number of positive DBS tests, n	XXX
Number of confirmatory DBS samples received, n	XXX
Number of positive confirmatory DBS tests, n	xxx
Number of confirmatory WB samples received, n	xxx
Number of positive confirmatory WB tests, n (%)	xxx (xx%)
Sensitivity	XX.X
Specificity	XX.X
Positive predictive value	XX.X
Negative predictive value	XX.X
Lin's Concordance Correlation Coefficient ^a between Confirmatory WB and Confirmatory DBS Testing	X.XXX
N= Number of participants in DBS arm with available samples for the Concordance analysis. Positive predictive value=Number of positive confirmatory whole blood tests / Number of positive	DBS tests.

^a Lin's Correlation between the Confirmatory WB and Confirmatory DBS Testing results (IU/mL).

Table 39: Mechanism of Non-Compliance - Mobile Technology DBS Testing Reminder Failures

Statistic	DBS (N=X)
Failed notifications, n	xxx
Participants with failed notification, n	XXX
Failed notification per participant for those with failed notifications, Median [Min, Max]	xxx [xxx, xxx]
Missed recommended tests, n	XXX
Participants with missed recommended tests, n	XXX
Missed recommended tests, with failed notifications within 7 days, n	XXX
Participants with missed recommended tests, with failed notification within 7 days, n	XXX
Number of Missed recommended tests per participant, Median [Min, Max]	xxx [xxx, xxx]
Number of missed recommended tests with failed notification within 7 days per participant, Median [Min, Max]	xxx [xxx, xxx]
N=Number of participants in the DBS arm in the ITT population.	1

Table 40: Mechanism of Non-Compliance to DBS Collection- Sample Failures

Statistic	DBS (N=X)
Missed recommended tests, n	xxx
Participants with missed recommended tests, n	xxx
Missed recommended tests, with failed sample collection, n	xxx
Participants with missed recommended tests, with failed sample collection, n	xxx
Missed recommended tests, with failed sample delivery, n	xxx
Participants with missed recommended tests, with failed sample delivery, n	xxx
Unevaluable samples, n	xxx
Participants with unevaluable samples, n	xxx
Note: N=Number of participants in the DBS arm in the ITT population. ^a An unevaluable sample is the equivalent of sample viability failure.	

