11.1.2 Secondary Endpoint

As a secondary endpoint we will be comparing the incidence of late CMV disease by one year post HCT between the two randomized groups using competing risk regression with death treated as a competing risk event ⁴². Using similar methods, we will also compare the CMV disease incidence of trial participants compared to subjects who received HCTs at the clinical sites in the similar time period but did not participate in the trial. As expected, the planned trial would not be sufficiently powered to detect a difference in late CMV disease incidence from 8% (current standard care) to 2% (observed in clinical trial). A trial powered for that detectable effect size would require 330 subjects to have 80% power (one-sided p values 0.05).

To determine the rate of CMV disease at participating sites during the clinical trial we will collect concurrent retrospective baseline data as well as CMV disease and survival data from subjects that were eligible for randomization but decided not to participate (the majority of subjects return to the transplant center at one year). The purpose of this analysis is to determine whether the subjects who participated in the trial are representative of the population at risk for late CMV disease and whether the phenomenon of late CMV disease continues to occur throughout the study period.

To assess the correlation of CMV viral load between DBS and plasma samples, we will use linear model. Other outcomes will be tabulated and compared between groups using Chi-Square, Fisher's exact, and log rank tests, as appropriate.

The relative contribution of mobile phone reminders, subject adherence to the device, and failures of the testing kit itself will be analyzed among subjects randomized to the DBS arm who did not reach the 90% adherence threshold.

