3.3.8. Scheduled DBS Tests

Participants in the DBS arm were instructed to collect DBS on the same day and at approximately the same time each week (Sunday through Wednesday to avoid delays due to weekend shipping). If a DBS sample PCR result is missing, it is considered as noncompliant to the scheduled DBS test, i.e. missed recommended DBS tests.

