3.3.11. Mobile Technology Reminder Failure

A Mobile Technology Reminder or Device Failure will be analyzed as one of the possible mechanisms for participants in the DBS arm to have non-compliance to the weekly DBS collection schedule. This failure will be defined as the occurrence of a failure to deliver the weekly DBS monitoring reminder message which may have prevented the scheduled monitoring test from being performed. The record of whether the weekly DBS monitoring reminder was sent is automatically generated by the Electronic Data Capture (EDC) system and stored in the Sent Notification eCRF.

For participants receiving both email and text message reminders, a failure is deemed to occur if either the email or text message was not sent. If the participant did not select a standard service provider, then only email notifications could be sent. The type of notification, i.e. whether it is the first or second reminder for an expected DBS test, is also saved. A second DBS reminder should be sent to a participant if a DBS test result record has not been uploaded within 4 days of their scheduled DBS test reminder. Because the second DBS

reminder could not be sent if the initial notification failed, descriptive analyses of device failures will be restricted to the status of the initial notification.

Failures will be identified by determining whether there are any days when a notification should have been sent, for which there is no record in the Sent Notification eCRF indicating that an initial reminder was sent. Participants in the DBS arm recorded their preferred day of the week for receiving the reminder on the DBS Testing Reminder eCRF. Participants were able to update the preferred day by submitting additional eCRFs. A failure is represented when there is no record in the Sent Notification eCRF where the recorded reminder date is the expected reminder date, and the reminder sequence number for the week is the first reminder.

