13. MOBILE TECHNOLOGY, DEVICE AND SHIPMENT EVALUATION

Mobile technology, device and shipment evaluation will include summaries of time from scheduled pick-up at participant residence to arrival at lab, the number of samples unevaluable due to lack of amplification or inhibition, and number of mobile technology failures.

The number of DBS testing reminder failures will be summarized (Table 39). The number of failed reminders overall, number of participants who had failed reminders, and the number of failed reminders per participant will be presented. In addition, the number of participants who missed a recommended DBS test following a failed reminder and the number of tests missed following failed reminders will be summarized. A listing presenting the DBS testing reminder configuration data is presented in Listing 10.

The number of samples with collection time, shipment time and arrival time entered, as well as the mean, standard deviation, minimum, maximum and median hours from scheduled pick-up to arrival at study laboratory will be summarized by transplant site and participants' perceived ease of access to blood draw facility for the participants in DBS arm (Table 36).

The number and proportion of unevaluable samples, and the number and proportion of participants with unevaluable samples, will be summarized by transplant site. (Table 37).

The Lin's concordance correlation coefficient will be calculated (Table 38). Sensitivity, specificity and predictive values of CMV detection in confirmatory DBS versus confirmatory WB testing will be reported. In addition, a correlation between the confirmatory DBS result and the confirmatory WB result will be visualized in Figure 5. A Bland-Altman plot of difference between the confirmatory DBS result and the confirmatory WB result will be presented in Figure 6.

For sample collection and sample delivery failures, the total number of failures, the number of participants with failures and the median, minimum and maximum number of failures per participant will be summarized by sample type, i.e. DBS, WB or any sample, in Table 40.

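### SAP Table 39 counts missed DBS tests that coincide with a failed reminder, but gives no tests expected, reminders sent or failed-versus-sent comparison, so it cannot by itself tell coincidence from an association with reminder failure.

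*SAP*

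**What the plan says.** - **Aim.** Protocol 11.1.2 states that "The relative contribution of mobile phone reminders, subject adherence to the device, and failures of the testing kit itself will be analyzed", and restricts this to DBS-arm subjects who fall short of the 90% adherence threshold. Exploratory objective 2 (Protocol 3.1.4, SAP 3.1.3) is to assess why a DBS result is missing, and names reminder, collection, delivery and viability failures.
- **Planned analysis.** SAP 13 says that "the number of tests missed following failed reminders will be summarized". It describes no comparison with weeks in which the reminder went out.
- **Table 39.** The test-level rows are "Failed notifications, n", "Missed recommended tests, n" and "Missed recommended tests, with failed notifications within 7 days, n". The others are participant counts and per-participant medians. The footnote gives the only denominator: "N=Number of participants in the DBS arm in the ITT population".
- **Definitions.** On a missed test, SAP 3.3.8 says "If a DBS sample PCR result is missing, it is considered as noncompliant to the scheduled DBS test". SAP 3.3.11 records a failure when either the email or the text was not sent to a participant who chose both, and says that "descriptive analyses of device failures will be restricted to the status of the initial notification".
- **Table 40.** This lists missed tests with a collection or delivery failure and, separately, unevaluable samples. It has no number of tests expected and no row for misses without any recorded failure.

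**The concern.** A count of misses that fall near a failed reminder mixes two things: misses that would have happened anyway, and any excess linked to the failure. Separating them requires the miss rate in weeks when the reminder was sent. Table 39 supplies neither that rate nor the total from which to derive it.

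Reminders are a named part of the intervention (SAP 4.4.2), and the protocol undertakes to analyse their relative contribution to non-adherence. If only coincidence counts are reported, a reader may take a non-zero figure as misses due to reminder failure, or a small one as evidence that reminders do not matter. The table supports neither reading.

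**Working it through.** **1. Size of the absent denominator.** The protocol's example in 11.1.1 is 38 weekly tests after discharge at day 100. The SAP Appendix 4 formula reproduces it: floor((365 − 100 + 1)/7) = floor(266/7) = 38. It also reproduces Appendix 4 Example 1: floor(305/7) = 43. Protocol section 4 anticipates 26 to 43 weeks of participation. For 100 DBS participants, tests expected (T) therefore run from 100 × 26 = 2,600, through 100 × 38 = 3,800, to 100 × 43 = 4,300. Removing hospital time would lower these figures.

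**2. What can be formed from Table 39.** Let F be failed reminders, M missed tests, and MF missed tests with a failed reminder. Assume that each reminder belongs to one test.

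- Miss risk after a failed reminder = MF/F. Available.
- Miss risk after a sent reminder = (M − MF)/(T − F). Not available, because T is absent.
- Overlap expected by chance = F × M/T. Not available.
- Overall miss rate = M/T. Not available.

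**3. The same entries under different T.** The documents contain no results, so these counts are assumed: F = 100, M = 700, MF = 25. Risk after a failed reminder is 25/100 = 25.0% throughout.

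| T | Chance overlap, 100 × 700/T | Risk after sent, 675/(T − 100) | Ratio of risks | Overall miss rate |
|---|---|---|---|---|
| 2,600 | 26.9 | 675/2,500 = 27.0% | 0.93 | 26.9% |
| 3,800 | 18.4 | 675/3,700 = 18.2% | 1.37 | 18.4% |
| 4,300 | 16.3 | 675/4,200 = 16.1% | 1.56 | 16.3% |

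Identical Table 39 entries fit either no association or a raised risk, depending on a row that is not there.

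**4. Coincidences when reminders have no effect.** Take T = 3,800, with 5% of reminders failing and 20% of tests missed regardless (both assumed). Then F = 190, and 190 × 0.20 = 38 misses coincide with a failure. If failure doubled the miss risk, the count would be 190 × 0.40 = 76. For failure rates of 1% to 10% and miss rates of 10% to 40%, the no-effect count runs from 3,800 × 0.01 × 0.10 = 3.8 to 3,800 × 0.10 × 0.40 = 152.

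**5. The window.** SAP 13 counts misses that come after a failed reminder. Table 39 uses a 7-day window with no direction. With weekly reminders, 5% failing at random (assumed), the share of misses with a failure in the window by chance is 1 − 0.95 = 5.0% if the window spans one reminder, 1 − 0.95² = 9.8% if two, and 1 − 0.95³ = 14.3% if three.

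**6. What Table 37 adds.** Table 37 gives DBS samples received and unevaluable for the same population. If each received sample matches one scheduled week, T is about M + received, less unevaluable samples if those already count as missed. With assumed values of 3,150 received, 50 unevaluable and M = 700, the overall miss rate is 700/(3,150 − 50 + 700) = 700/3,800 = 18.4%, or 700/3,850 = 18.2% if unevaluable samples are not counted as missed. The middle row of step 3 could then be formed, crudely.

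**7. Unevaluable samples.** Objective 2 treats viability failure as a cause of a missing result, which would make an unevaluable sample a missed test. Footnote b of SAP Table 5 instead counts unevaluable samples among those with laboratory results. Table 40 does not say which convention its missed-test row follows.

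**The case against.** The strongest reply is that nothing more than description was intended. The exploratory outcome measure is a number of failures. SAP 3.3.11 says only that a failed reminder may have prevented the test, and no causal claim is planned. That is correct and sets the weight of the point. It does not remove it, because Protocol 11.1.2 promises a relative contribution, and counts without a comparator do not describe one.

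The second reply is that the information exists elsewhere. This also stands in part. Table 37 combined with Table 39 gives a crude miss rate and a crude contrast. Listing 10 shows each expected reminder and whether it was sent, and Listing 9 shows each DBS result. But a reader would have to assemble the comparison under an unstated one-sample-per-week assumption.

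The third reply is that a failed-versus-sent contrast is not randomised. A week counted as failed may still have had one of two messages delivered, so a confidence interval would not isolate a reminder effect. This is right. The contrast should be labelled as an association and the partial failures shown separately.

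**Conclusion.** The point holds as a minor defect of tabulation. Table 39 alone cannot separate coincidence from a reminder association, and no planned table makes the comparison. Under the assumed counts, the ratio of risks moves from 0.93 to 1.56 across the documents' own range of follow-up. The failure rates, miss rates and counts are illustrative, and the calculation links one reminder to one test.

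Three stronger readings are tempting but not supported:

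- A reader might infer that no DBS miss rate can be obtained from the planned outputs. That is true of Table 39 read alone, but Table 37 and Listings 9 and 10 allow one.
- A reader might infer that participant non-collection is never shown. Table 33 reports self-declared missed collections and reasons such as being too busy, unwell or without a caregiver, although only at one month after discharge.
- A reader might infer that viability failure is left out. Table 40 reports it as unevaluable samples; what is missing is whether those are included in the missed-test count.

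The primary endpoint rests on clinician-recommended tests, so neither it nor the power is affected.

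**What to change.** **Table 39**

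- Add DBS tests expected, with hospital time removed as in SAP 3.3.2, and initial reminders due and sent.
- Add n/N (%) missed in weeks with the initial reminder sent and in weeks with it failed, and the difference with a participant-clustered 95% CI. Label it a non-randomised descriptive association.
- Present it for the whole DBS arm and for DBS participants below the 90% threshold, as Protocol 11.1.2 specifies. Footnote that the SAP's threshold is defined on clinician-recommended tests.
- Link each test to the reminder that precedes it in its own week, in line with SAP 13, in place of the undirected 7-day window.
- Show separately the weeks in which only one of email or text failed.

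**Table 40**

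- State whether unevaluable samples are included in missed tests.
- Add a row for misses with no recorded reminder, kit, delivery or viability failure. Footnote that shipment data are entered by participants and may be incomplete, so this row is not the same as not collected.
- Report overlaps between causes as overlaps. A mutually exclusive ranking of causes should be avoided, because it would assign coincidental misses to reminder failure.

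**Cost.** A few table rows and one short analysis of reminder, shipment and laboratory records already collected. The downside is a contrast open to confounding, which the label must make plain.
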